## **2. Data analysis and monitoring.**

Statistical processing of the obtained data will be carried out using the application package STATISTICA version 7.0, taking into account computational methods recommended for biology and medicine. Statistical research methods include: calculation of median and mode, standard deviation. To determine the reliability of the obtained indicators, Student's t-test will be used. Also calculate the pairwise correlation coefficient according to Pearson.

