## **Methods of statistical data analysis**

All patients hospitalized for special treatment with a verified diagnosis of a malignant neoplasm were subjected to the study in the abdominal department of the KGP at the Regional Oncological Dispensary, Karaganda.

The quantitative and qualitative indicators obtained during the study were analyzed using descriptive and analytical statistics methods. For statistical processing of qualitative (diagnosis codes, dichotomous data) and quantitative variables: symptom intensity, severity, frequency of occurrence, we used the calculation of the median level (Me) with 25%-75% quartiles (Q25; Q75) and the calculation of the arithmetic mean (M) with error (m) and 95% confidence interval (95% CI), standard deviation (s). Quantitative variables were checked for normality of distribution using the Kolmogorov-Smirnov test, as well as the module of Skewness and Kurtosis for quantitative variables  $| \leq 2 |$ . Differences in the 3 groups of patients for quantitative variables corresponding to a normal distribution were identified using the Student's t test for unrelated groups, first for 3 or more groups, and then in pairs for each pair using the Student's t test. Differences for rank variables, or quantitative but not normally distributed for unrelated groups, were determined by the Kruskal-Wallis test or median test for 3 groups, and then pairwise or non-parametric Mann-Whitney test for each of the 3 pairs (groups 1 and 2, groups 1 and 3, groups 2 and 3), and for related groups (dynamic observations) by the Kendall test for 3 groups and then by the Wilcoxon test (Wilcoxon) for each of the 3 pairs (baseline, after 5 days and after 10 days).

Correlation was performed for quantitative variables according to Pearson and for rank variables according to Spearman. Statistical processing of the results was carried out using the Statistica program version 10.

**Results and discussion.** The nutritional status of patients in all three groups before surgery and during the 10-12 days of the postoperative period according to the methods of assessing nutritional status NRS, SGA and NRI was assessed as normal, moderate and severe malnutrition

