A comparative analysis of the dynamics of ALT and ASAT values in all patients in the study groups on the 2-3, 6-8, 10-12 days of the postoperative period reflected an excess of their normal values after surgery in some patients tens of times in the first day of the postoperative period. These changes can be explained, first of all, by the surgical intervention itself and its volume, the underlying disease of the hepatopancreatoduodenal zone and the associated cytolytic syndrome against the background of cholestasis [9,10,11].

In terms of assessing the dynamics of blood transaminase levels, in the majority of patients in the first group (78.2%), by the 5th and 10th days there was a decrease in ALT and AST values, on average, by 32.1 and 40.15%, respectively.

In the overwhelming number of patients in the second group (81.6%,  $n=26$ ), a statistically significant decrease in the level of these blood transaminases was also recorded, on average by 72.2% by the fifth day and 66.7% by the 10th day of the postoperative period from level of their initial indicator.

With a mixed type of nutritional support, by the 5th day of the postoperative period, the average significant decrease in transaminases was, on average, up to 72.6% of the initial values ( $p = 0.000$ ); by the 10th day of the postoperative period, their level decreased to 63.8% from the previous achieved value of 5 days ( $p=0.008$ ).

When comparing analyzes of the level of total blood bilirubin in patients of all nutrition groups, there was a strong direct correlation with a decrease in the level of blood transaminases, which, apparently, was also due to the creation of sufficient intraoperative bile outflow due to drainage of the biliary tract and elimination of the cause of obstructive jaundice (tumor).

However, high values of total blood bilirubin that persisted on the first day after surgery were due to temporary swelling of the biliary tract, which caused the excess of the norm by more than 10 times ( $p = 0.000$ ).

On days 5-7, there was a tendency towards a 5-6 fold decrease in its level from the initial values, which gradually decreased to normal values by days 10-12 and in some patients persisted until discharge from the hospital ( $p = 0.004$ ).

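### The correlation rule ignores the normality check that the same section applies to group comparisons, so skewed liver markers would be correlated by Pearson on the raw scale (minor)

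*Combined protocol and SAP*

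**What the plan says.** The protocol, section III.2 (Data analysis and monitoring), names one correlation method and sets no condition on distribution: "Also calculate the pairwise correlation coefficient according to Pearson".

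The report, under Methods of statistical data analysis, splits the methods by type of variable: "Correlation was performed for quantitative variables according to Pearson and for rank variables according to Spearman".

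The same section has a normality check: "Quantitative variables were checked for normality of distribution using the Kolmogorov-Smirnov test", together with limits on skewness and kurtosis. It uses the result for group comparisons: "Differences for rank variables, or quantitative but not normally distributed for unrelated groups, were determined by the Kruskal-Wallis test" (or a median test), followed by pairwise Mann-Whitney tests. Nothing carries that switch over to correlations.

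Under Results and discussion, the ALT and AST values "reflected an excess of their normal values after surgery in some patients tens of times in the first day of the postoperative period". For bilirubin, the swelling of the biliary tract is given as the reason "which caused the excess of the norm by more than 10 times". For bilirubin in patients of all the nutrition groups, the report then states that "there was a strong direct correlation with a decrease in the level of blood transaminases". It gives no coefficient, confidence interval, sample size, day or method with that statement.

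**The concern.** Pearson's coefficient uses squared distances from the mean. On strongly right-skewed data, the few patients with the largest values carry most of the weight. If those patients are high on both markers, the coefficient can be large even when the markers are unrelated in everyone else. The statistical section recognises this kind of problem for group comparisons and moves to ranks, but it leaves correlations on the raw scale.

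What is at stake is how the reported bilirubin-transaminase relation should be read. It falls within the liver-function part of objective 2, and the report goes on to offer restored bile outflow as a likely explanation. As the rule stands, a reader cannot tell whether the relation holds across the cohort or reflects a handful of patients.

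**Working it through.** **Step 1: the two rules side by side.** This step needs no assumption.

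| Variable | Group comparison | Correlation |
|---|---|---|
| Quantitative, passes the normality check | Student's t | Pearson |
| Quantitative, fails the normality check | Kruskal-Wallis or median test, then Mann-Whitney | Pearson |
| Rank | Kruskal-Wallis or median test, then Mann-Whitney | Spearman |

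The second row is the inconsistency. Protocol section III.2 is narrower still, because it has no rank alternative at all.

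**Step 2: is there a figure to reproduce?** No. The documents give no r, and no SD for bilirubin, ALT or AST. The size can only be shown as a range over assumptions.

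**Step 3: one patient extreme on both markers, closed form.** Inputs from the documents: n=91 in total, 30 or 31 per group, bilirubin more than 10 times normal, transaminases tens of times normal. Assumed: the other n-1 patients have zero correlation and a common SD s (in multiples of normal), and one patient lies dx=10 and dy=30 above them. With c=(n-1)/n,

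r = c·dx·dy / √{[(n-2)s² + c·dx²]·[(n-2)s² + c·dy²]}

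For n=91 and s=1: c=0.989, numerator 0.989×300=296.7, first bracket 89+98.9=187.9, second bracket 89+890.1=979.1. So r = 296.7/√(187.9×979.1) = 0.69.

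| s (times normal) | 1 | 2 | 3 | 5 |
|---|---|---|---|---|
| r, n=30 | 0.87 | 0.64 | 0.46 | 0.26 |
| r, n=91 | 0.69 | 0.39 | 0.24 | 0.11 |

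**Step 4: Spearman on the same kind of data.** If one patient has the top rank on both markers and the others are unrelated, that patient's rank deviation is (n-1)/2 on each marker and the others average -1/2. The expected coefficient is

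[(n-1)²/4 + (n-1)/4] / [n(n²-1)/12] = 3/(n+1)

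That is 3/92 = 0.03 for n=91 and 3/31 = 0.10 for n=30, whatever the spread and however extreme the patient. Simulation gives the same values.

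**Step 5: skewed data, simulated.** Two unrelated log-normal markers, n=91, one patient set to 10 or 20 times the median on both, 4,000 data sets per cell. Median Pearson r:

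| Log-SD (assumed) | 10 times on both | 20 times on both | Spearman |
|---|---|---|---|
| 0.7 | 0.47 | 0.80 | about 0.03 |
| 1.0 | 0.17 | 0.50 | about 0.03 |
| 1.3 | 0.03 | 0.19 | about 0.03 |

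Three patients at 20 times the median on both give 0.92 (log-SD 0.7) or 0.74 (log-SD 1.0), against about 0.10 for Spearman. A patient at 20 times the median on one marker and average on the other gives r close to zero, about -0.03 to -0.04.

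**Step 6: skewness alone.** With unrelated log-normal markers (log-SD 0.8 to 1.5) and no planted patient, r reaches 0.7 or more in at most 0.9% of data sets at n=30 and 0.2% at n=91. The test of zero correlation rejects in 4.7% to 5.9%, so type I error is essentially intact.

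**The case against.** A reader might go further and infer that one extreme patient produced the reported correlation. The documents do not support that, for four reasons.

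- The effect needs the other patients to vary little. Across 91 patients, a single patient approaches r=0.7 in step 3 only if the SD of the rest is about 1 times normal or less, and no SD is given.
- The report quotes multiples of normal, not of the cohort median. It does not limit the high bilirubin to a few patients, so the median may itself be raised, and 20 times the median may be far beyond anything observed.
- It does not say that the same patients were extreme on both markers. If they were not, there is no inflation.
- It refers to several patients with extreme transaminases. That cuts both ways: a wider spread weakens the one-patient effect, but several patients high on both markers would strengthen it.

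Three other inferences also go too far. That Pearson on raw values was used for this result is inferred from the stated rule; the result itself names no method, and it refers to a decrease in transaminases, whereas the extreme values are first-day levels. That the groups were pooled is not stated; the wording could equally mean within each group. That a confidence interval for the correlation is wrong has no object, since none is planned or reported: the 95% CI in the methods section is mentioned with the mean.

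On importance, the correlation compares no arms, none of the report's three conclusions uses it, and the bile-outflow explanation is hedged and argues from drainage and removal of the obstruction. The report also describes cytolysis together with cholestasis, so some real association is plausible.

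All of this stands, and it limits the impact. It does not remove the inconsistency in step 1 or the missing details of the reported result.

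**Conclusion.** The point holds as a minor one. The plan tests normality and acts on the result for group comparisons but not for correlations, and the protocol offers Pearson alone. Under that rule, markers with values tens of times normal would be correlated on the raw scale.

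The possible distortion ranges from negligible to large: for one patient among 91, a median r between 0.03 and 0.80 over the assumptions in step 5, against about 0.03 for Spearman. It rests on three things the documents do not state: the spread of the markers, whether the same patients were extreme on both, and that the markers are otherwise unrelated. The reported strong correlation is therefore not shown to be wrong. It is not shown to be robust either, because no coefficient, method, n or day is given. The report's conclusions are unaffected.

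**What to change.** In protocol section III.2 and the report's Methods of statistical data analysis, extend the existing normality rule to correlations: Pearson for quantitative variables that pass the check, and Spearman for rank variables and for any quantitative variable that fails it, including bilirubin, ALT and AST if they fail.

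Recompute the bilirubin-transaminase correlation under that rule, with one value per patient per day. State whether levels or changes are correlated, and report the method, coefficient, 95% CI, n and day. Keep the description as strong only if the rank coefficient supports it.

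The cost is one sentence in each section and a re-run on existing data. Spearman loses a little efficiency if a variable that failed the check is in fact close to normal.

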### **3. Data storage and confidentiality.**

Confidentiality is ensured by encrypting the personal data of the subject with a digital code. Storage of information about patients is carried out in writing in the registration journal of the research topic, in electronic form on a computer in the databases of Microsoft Excel and STATISTICA 7.0 programs. The head and executor of the research topic have access to the data. The results of the research, without indicating personal data, will be used to write a doctoral dissertation, the results of the research will be published in print and electronic publications and reported at conferences.

## **IV. Risk/benefit assessment**

### **1. Degree of risk.**

When conducting research, the degree of risk is minimal. Before the study, participants will be interviewed to explain the purpose and methods of the study. Minimal risk means that the likelihood and magnitude of harm or discomfort expected in the study is no greater than would normally be encountered in everyday life or while receiving routine physical or psychological tests. The study will be conducted in compliance with all requirements and safety measures.

### **2. Potential risk.**

During the study, exacerbation of pre-existing, chronic diseases is possible. In this case, the patient is excluded from the study and all necessary support and correction measures are taken.

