### **5. Criteria for inclusion.**

- patients or relatives who consented to participate in the study (informed consent).
- patients with concomitant diseases (cardiovascular disease, liver and kidney dysfunction, lung diseases) that may complicate the course of the operation and the postoperative period, or patients who have previously undergone various operations.

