### **6. Criteria for exclusion.**

- age up to 20 years, pregnant and lactating
- patients with an unstable condition, unstable hemodynamics or severe concomitant pathology in the acute stage.

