## **1. Methods and procedures.**

At the first stage, modern ideas about methods for assessing nutritional status and methods of nutritional support in the early postoperative period of patients operated on for malignant tumors of the hepatopancreatoduodenal zone were studied.

At the second stage, taking into account the need to select the optimal method of nutritional support in the early postoperative period, patients underwent an intragroup and intergroup comparative analysis of the main clinical and laboratory indicators, reflecting the most satisfactory dynamics of plastic processes regarding the type of nutritional support: enteral, parenteral and mixed.

To solve these problems, a prospective, longitudinal, parallel study and retrospective analysis of the results of treatment of 91 patients with malignant tumors of the hepatopancreatoduodenal zone who underwent the following operations were carried out:

- 1) resection of various segments of the liver;
- 2) hemihepatectomy;
- 3) transhepatic drainage of the right and left hepatic duct;
- 4) bypass gastroenteroanastomosis or cholecystoenteroanastomosis with interintestinal enteroenteroanastomosis according to Brown;
- 5) gastro-pancreatoduodenal resection;
- 6) corporecaudal resection of the pancreas with splenectomy.

The study was carried out on the basis of the KGP at the RVC "Multidisciplinary Hospital No. 3 of the city of Karaganda". Venue: intensive care unit.

To identify nutritional deficiencies, there are screening methods recommended by the international clinical nutrition associations ASPEN (American Society for Parenteral and Enteral Nutrition - ASPEN) and ESPEN (European Society for Parenteral and Enteral Nutrition - ESPEN), including questioning patients, using standard anthropometric and laboratory data, which makes it possible to assess nutritional status and the degree of its impairment.

At the first stage, the clinical condition of the patient was assessed using the Nutritional Risk Screening (NRS, 2002), Subjective Global Assessment (SGA) and Nutritional Risk Index (NRI) protocols before surgery and on the 5th, 10th, 15th day after surgery .

A comparative assessment of the clinical effectiveness of the use of types of nutritional nutrition in a complex of therapeutic measures after these operations in the hepatopancreatoduodenal zone was carried out.

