Some nutritional status indicators available for determination at the Oncology Clinic were assessed - body mass index (weight measurements were carried out before surgery, on the 5th, 10th and 15th days), basal metabolic rate (calculated using the Harris-Benedict equation, based on anthropometric data of the patient (gender, age, weight and height).), laboratory parameters: blood hemoglobin, lymphocytes, total protein, serum albumin, serum transferrin, total bilirubin and direct, ALT, AST, which are related to the traditional method for assessing nutritional status.

Additionally, we assessed the duration of postoperative gastostasis, the timing of the onset of intestinal motility, the appearance of stool, the return to a normal diet, the length of patients' stay in the ICU, the readmission of patients to the ICU and the duration of the postoperative bed-day, and the incidence of complications was calculated.

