### **3. Protection from risk.**

This procedure is introduced voluntarily and participants or other legal representatives of the patient have the right to refuse the examination. In order to exclude exacerbations of pre-existing chronic diseases, a thorough medical history will be taken and concomitant pathology taken into account.

**4.** The potential benefit for the participant is the possibility of early nutritional support in cancer-surgical patients, receiving timely recommendations on lifestyle management, prevention, treatment and rehabilitation.

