### Scientific hypothesis

Complete and comprehensive nutritional support for patients operated on for malignant neoplasms of the hepatopancreatoduodenal zone, in the form of various approaches and methods of delivering nutrients to patients in the early postoperative period, allows to improve the functional activity of the gastrointestinal tract of patients, stabilize the level of carbohydrate, protein, basal metabolism, accelerate transfer to full enteral nutrition and reduce the length of stay in the intensive care unit and, ultimately, in the hospital.

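### Patients whose chronic disease flares are to be excluded from the study, and no available text keeps them in outcome follow-up or in the analysis

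*Combined protocol and SAP*

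**What the plan says.** Protocol section IV.2 (Potential risk) says that a pre-existing chronic disease may flare while the study is under way, and continues: "In this case, the patient is excluded from the study and all necessary support and correction measures are taken". What it promises afterwards is care. It mentions neither further assessment nor analysis.

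The rule is separate from selection. Section II.6 already bars "patients with an unstable condition, unstable hemodynamics or severe concomitant pathology in the acute stage", and section IV.3 adds a preventive step: "In order to exclude exacerbations of pre-existing chronic diseases, a thorough medical history will be taken and concomitant pathology taken into account". Section II.5 lists among the inclusion criteria "patients with concomitant diseases (cardiovascular disease, liver and kidney dysfunction, lung diseases) that may complicate the course of the operation and the postoperative period", so flares are foreseeable in the enrolled population.

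Nutritional status is assessed "before surgery and on the 5th, 10th, 15th day after surgery" (section III.1). The same section lists liver tests and, among further outcomes, ICU stay, "the readmission of patients to the ICU and the duration of the postoperative bed-day, and the incidence of complications was calculated". The report repeats this list under Clinical research program. Its Scientific hypothesis includes the expectation that nutritional support will "reduce the length of stay in the intensive care unit and, ultimately, in the hospital". Objective 2 concerns protein and carbohydrate metabolism and liver function.

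**The concern.** A flare of liver, kidney, heart or lung disease after a major abdominal operation is plausibly tied to what the trial measures. It may prolong ICU or hospital stay, alter transaminases or bilirubin, or worsen nutritional status. Read plainly, the rule takes such patients out because of something that happened after entry. The groups then compared are no longer the groups that started feeding, but those who got through without a flare.

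If flares differ between the enteral, parenteral and mixed groups in number, type or prognosis, the exclusions can shrink, reverse or create a difference. If they do not differ, or nobody was excluded, this rule does not distort the between-group comparison.

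**Working it through.** **1. Is there a retention rule elsewhere?** The places where one would be expected:

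| Place | What it covers | Follow-up or analysis of excluded patients |
|---|---|---|
| Protocol III.2, Data analysis and monitoring | software, descriptive statistics, t-test, Pearson correlation | nothing stated |
| Protocol III.3, Data storage and confidentiality | "Storage of information about patients is carried out in writing in the registration journal of the research topic", plus electronic databases | no exception for excluded patients; nothing on analysis |
| Protocol IV.3, IV.5 and V | right to refuse, consent | nothing stated |
| Report, Methods of statistical data analysis | tests by type of variable | no analysis set, no rule for missing or withdrawn patients |

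The gap is therefore continued assessment and the analysis set, not the keeping of data already collected. The consent appendix is not available to this review, so this holds for the available text only.

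**2. When can the rule bias the comparison?** Consent and baseline tests precede surgery; the feeding compared is postoperative (II.1, III). A flare between consent and surgery cannot be caused by the feeding. The concern is with flares after surgery. Section IV.2 does not separate the two.

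**3. Do the reported counts show losses?**
- Enrolled: 31 + 30 + 30 = 91, in both protocol and report.
- NRI before surgery: 62 + 26 + 3 = 91. This is a baseline count and cannot show who remained at day 5, 10 or 15.
- Parenteral group at days 10-12: 17 normal + 14 moderate = 31, against n = 30.
- Second group, transaminases: 26 patients given as 81.6%, and 26/0.816 = 31.9, against n = 30 (26/30 = 86.7%).

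The later figures show no shortfall, but they disagree with the group size and cannot settle the matter.

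**4. How much could it matter?** The documents give no figure to reproduce. Only n = 30 (second and third groups) comes from them; everything else here is assumed. A flare is not itself counted as a complication.

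*Complications.* Assume 6 patients with a complication in each group, 1 flare in the second group and 3 in the third, all excluded. Let f be the number with a flare and o the number of those who also had a complication. The rate is 6/30 before exclusion and (6 - o)/(30 - f) after it. Differences are third group minus second.

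| Assumption | All patients | After exclusion | Difference |
|---|---|---|---|
| f = 1 vs 3, all with a complication | 6/30 vs 6/30 | 5/29 = 17.2% vs 3/27 = 11.1% | 0 becomes -6.1 points |
| f = 1 vs 3, none with a complication | 6/30 vs 6/30 | 6/29 = 20.7% vs 6/27 = 22.2% | 0 becomes +1.5 points |
| f = 3 vs 3, all with a complication | 6/30 vs 6/30 | 3/27 vs 3/27 = 11.1% | stays 0, but both rates fall from 20.0% |
| no exclusions | 6/30 vs 6/30 | unchanged | stays 0 |

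*Means (stay or laboratory values).* If excluded patients average d units above the rest of their group, excluding f of 30 lowers that group's mean by f × d/30. With 1 vs 3 exclusions and the same d, the between-group difference shifts by (3 - 1) × d/30 = d/15. For bed-days, d = 5, 10 or 15 gives 0.33, 0.67 or 1.00 day.

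**The case against.** **The sentence is a safety statement and may mean only leaving study procedures.** That reading is possible, and it is a reason to clarify. The words as they stand say excluded from the study, and no available text narrows them.

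**The report points towards full follow-up.** Results and discussion describes transaminases in all patients at days 2-3, 6-8 and 10-12, and Conclusion 2 speaks of 100% of patients throughout nutritional support. This stands as evidence against large losses. It is not decisive, because all may mean all who remained, and the later counts do not agree with n = 30.

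**The worked outcomes have no reported result.** This is correct for the available text (one figure is not shown): no complication, ICU or bed-day comparison is given, and these outcomes are described as additional. However, stay is in the hypothesis, and the argument for means applies equally to the bilirubin and transaminase results that are reported.

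**The magnitudes are invented.** They are assumptions and show only direction and order of size.

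A reader might infer more than the documents support:
- *That excluded patients' data were thrown away.* Section III.3 stores patient information without exception, and nothing mentions deletion. Stay and readmission might also be recoverable from medical records, which the study plan already uses.
- *That every flare is a complication the trial failed to count.* No available section classes it so.
- *That the 31-against-30 count shows exclusions or replacements.* It shows only that the count is inconsistent.

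**Conclusion.** The concern holds as a gap in the plan. Section IV.2 excludes patients on a post-entry event, and the available text keeps them neither in outcome follow-up nor in the analysis. For flares after surgery this can bias the comparison in either direction. Calling the event outcome-related is an inference from the diseases in II.5 and the outcomes in III.1; the documents do not say it.

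The true size cannot be computed. On the assumed counts, two more exclusions in one group than in the other shift a complication difference by 1.5 to 6.1 points and a mean by one fifteenth of the excluded patients' excess. With no exclusions the shift is zero, and it is also zero with equal exclusions of the same kind.

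It would be tempting to conclude that patients were removed and that the reported results are biased. The documents do not support this: no available text shows the rule being applied. Equally, they do not allow a reader to rule it out, because the number analysed after baseline is not clearly given.

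**What to change.** Leave the clinical care of an exacerbation as it is. Add one sentence to section IV.2 or III.2: stopping study procedures does not end outcome follow-up and does not remove the patient from the analysis. Define the analysis set as every enrolled patient who had surgery, in the nutrition group entered.

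Because the trial ended in March 2020, the practical step is in the report:
- Give the number excluded under this rule by group and time (before surgery, by day 5, 10 or 15), or state that there were none.
- Give the number analysed for each result, and reconcile the second-group counts with n = 30.
- Where outcome records of excluded patients exist, show results with and without them; where they do not, say so.
- Do not reclassify an exacerbation as a complication unless the trial's own definition does so.

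The cost is a small amount of extra reporting and, only if someone was excluded, retrieval of routine records. If nobody was excluded, one sentence closes the point. The change removes this source of bias only; it does not make the groups comparable in other respects.
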